Dose Escalation Safety Lead-In and Mid-Study Interim Safety Analysis	
Dose Escalation Safety Lead-In
 
1. If, at any time, 1 or more of the first 3 safety-evaluable patients experience grade 3 or higher treatment-associated adverse events within the first 30 days of initiation of treatment, then no further patients will be enrolled at the current dose level.2. After 6 patients have been enrolled on study, enrollment will be halted for 30 days for completion of the dose escalation lead-in safety analysis. If 0-1 patients experience grade 3 or higher treatment-associated adverse events within the first 30 days of initiation of treatment, then additional patients may be enrolled at the next dose level.3. If enrollment is halted at any time during the lead-in period due to treatment-associated adverse events, the UCSF DSMB will review all available safety data with the Principal Investigator. Based on this review, study discontinuation or reduction of the epacadostat dose may be recommended. No further patients will be enrolled on study without the approval of the DSMB. If the DSMB allows additional patients to enroll, the lead-in period will be repeated at the new dose level with a maximum of 6 additional patients enrolled prior to follow-up safety analysis. At the discretion of the DSMB, patients who are currently on study may continue treatment at the reduced dose level.4. Patients who discontinue treatment on study within 30 days of initiation of therapy for reasons other than treatment-associated toxicity will be deemed inevaluable for safety and replaced for safety analysis. 
Mid-Study Interim Safety Analysis (Stage 1)
 
Enrollment will also be halted for 30 days for interim safety analyses after a total of 30 safety-evaluable patients have initiated treatment on study in both Arms A and B. Patients who discontinue treatment on study within 30 days of initiation of therapy for reasons other than treatment-associated toxicity will be deemed inevaluable for safety and replaced for safety analysis. The study will be discontinued under the following circumstance:
 
1. On-study occurrence of 3 or more Grade 4 (life threatening) serious adverse events (SAEs) or deaths, which are deemed at least possibly related to the study agent.2. Based on the review of data the DSMB has serious concerns about the safety of patients on the study. In addition to stopping the study, the DSMB may recommend that the epacadostat dose for all patients be de-escalated for all current and future patients or cessation of further patient accrual.

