--	---

Duration of Therapy	
Dose Escalation Safety Lead-In Phase: 6 patients will receive triplet therapy for 30 days at Dose level 0. After 30 days of therapy, if those patients do not experience a DLT, an additional 6 patients will be enrolled at the next Dose level, Level 1 which will increase epacadostat to 600 mg for 30 days, tavo-EP and pembrolizumab will not be dose escalated. If no patients experience a DLT at 600 mg, that will be the dose level of epacadostat used in Stage 1, for both Arms A and B.
 
Dose Expansion Phase, Stage 1, Arm A: Patients will receive triplet therapy for 12 months or until the development of an unacceptable treatment associated toxicity or confirmed progression. After 12 months of therapy, patients will enter the follow-up phase for the next 24 months. Patients with disease progression during the follow-up phase will have access to 12 additional months of triplet therapy. Patients who are eligible for treatment on study but who have experienced regression of all previously accessible lesions may continue on pembrolizumab and epacadostat without tavo-EP.
 
Dose Expansion Phase, Stage 1, Arm B: Patients will receive combination therapy for 12 months or until the development of an unacceptable treatment associated toxicity or confirmed progression. After 12 months of therapy, patients will enter the follow-up phase for the next 24 months.
 
Dose Expansion Phase, Stage 2: Depending on the results of the clinical data in Stage 1, Stage 2 will enroll up to an additional 26 patients accordingly:
 
If there are at least ≥ 3 responses in 15 patients, in either Arms A or B, up to an additional 26 patients (13 patients in Arm A and 13 patients in Arm B) will be enrolled in the respective treatment arms.

Duration of Follow up	Patients will be followed at 3 month intervals for toxicity and radiographic imaging 1) until start of a new anti-cancer treatment, (2) until 30 days after documented disease progression, (3) until death, or (4) until 36 months from the initiation of treatment on study, whichever comes first. Each subject will be followed for overall survival until death, withdrawal of consent, or the end of the study, whichever occurs first.
Duration Of Study	Study accrual will be sufficient to assess the primary endpoint within 24 months from the time the study opens to accrual.

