4.3 Dose Limiting Toxicity (DLT) and Maximum Tolerated Dose (MTD)

If DLT is encountered during the first cycle, the following rules (see table below) will be applied. If no DLT is encountered at a given dose level, escalation will be continued to the next higher dose level. If no DLT is found at the highest cohort, this cohort will be considered the recommended Stage 1 dose for epacadostat.

Table 4-3: Dose Escalation Decision Rules - DLT and MTD

Number of Patients with DLT at a Given Dose Level	Escalation Decision Rule
0 out of 3	Escalate dose to next higher dose level
1 out of 3	Enter at least 3 more patients at this dose level If 0 of these 3 additional patients experience DLT (1 of 6), proceed to the next dose level If 1 or more of the 3 additional patients suffer DLT (2 of 6), then dose escalation is stopped and this dose is declared the maximal administered dose (highest dose administered) Determination of the MTD will continue at the next lowest dose cohort, at which an additional 3 patients will be added, for a total of 6 (unless that cohort already has 6 patients)

≥ 2 out of 3	Dose escalation will be stopped This dose level is declared the maximum administered dose The next lower cohort will be expanded to 6 patients If < 1 experience DLT, this dose is the maximal tolerated dose (MTD)
≤ 1 out of 6 at highest dose level below the maximum administered dose	This is generally the recommended Phase 2 dose At least 6 patients must be entered at the recommended Phase 2 dose

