4.3.1 Dose Limiting Toxicity

Adverse Events and other symptoms will be graded according to the NCI Common Terminology Criteria for Adverse Events Version 4.03 (NCI, CTC web site <http://ctep.info.nih.gov>).

A DLT will be defined as any one of the following adverse events occurring during Cycle 1 when association to therapy that is part of this study is related or possibly related:

1. Hematologic dose-limiting toxicity

- Grade 4 neutropenia lasting for ≥7 days in duration.
- Febrile neutropenia of any grade
- Grade 4 thrombocytopenia ($\leq 25.0 \times 10^9/L$) lasting for ≥7 days in duration.
- Grade 3 thrombocytopenia complicated by clinically significant bleeding and/or requiring platelet or blood transfusion

2. Non-hematologic dose-limiting toxicity

This will be defined as any Grade ≥3 non-hematologic toxicity, which is clinically meaningful and related with the specific **EXCEPTION** of:

- Any grade alopecia
- Grade 3 total hyperbilirubinemia if <35% is direct component
- Grade 3 transient ALT/AST elevation
- Grade 3 rash, nausea, vomiting or diarrhea for ≤ 3 days or is not properly managed with optimal supportive care
- Grade 3 lab abnormalities must be clinically significant, meaningful and dose related.

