Myocarditis	2	
Hold pembrolizumab and epacadostat until resolution to Grade 0. Monitor symptoms daily, hospitalize. Promptly start IV methylprednisolone 2 to 4 mg/kg/day or equivalent after Cardiology consultation has determined whether and when to complete diagnostic procedures including a cardiac biopsy. Once the patient is improving, gradually taper steroids over \geq28 days and consider prophylactic antibiotics, antifungals, or anti-PJP treatment (refer to current NCCN guidelines for treatment of cancer-related infections [Category 2B recommendation]). If toxicity rapidly improves to Grade 0, then the decision to reinitiate study drug/study regimen will be based upon treating physician's clinical judgment and after completion of steroid taper. If toxicity does not rapidly improve, permanently discontinue pembrolizumab and epacadostat.

Adverse Event	CTCAE v4.03 Grade	Action Taken
	3 or 4	Permanently discontinue pembrolizumab and epacadostat if related to these agents. Monitor symptoms daily, hospitalize. Promptly start IV methylprednisolone 2 to 4 mg/kg/day or equivalent after Cardiology consultation has determined whether and when to complete diagnostic procedures including a cardiac biopsy. Once the patient is improving, gradually taper steroids over \geq 28 days and consider prophylactic antibiotics, antifungals, or anti-PJP treatment (refer to current NCCN guidelines for treatment of cancer-related infections [Category 2B recommendation]).
Renal failure or nephritis	2	Treat with oral corticosteroids.
	3 or 4	Permanently discontinue pembrolizumab and epacadostat if related to these agents. Treat with systemic corticosteroids. When severity of the event improves to \leq Grade 1, steroid taper should be started and continued over no less than 4 weeks. If unrelated to pembrolizumab, treatment with pembrolizumab and epacadostat may be resumed once steroids have been discontinued.
Any toxicity, if clinically significant and not manageable by supportive care	2 or 3	Interrupt epacadostat and pembrolizumab if toxicity is attributed to epacadostat and pembrolizumab. When toxicity resolves to \leq Grade 1, resume pembrolizumab and epacadostat. For recurrent or persistent Grade 2 or 3 toxicity that is clinically significant and not manageable with supportive care, consider further dose reduction of epacadostat or epacadostat and pembrolizumab discontinuation.

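### The DLT exception for four grade 3 toxicities in section 4.3.1 is ambiguous and, as written, exempts events that are not properly managed, however long they last

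*Combined protocol and SAP*

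**What the plan says.** Section 4.3.1 opens the non-hematologic part of the DLT definition broadly: "This will be defined as any Grade ≥3 non-hematologic toxicity, which is clinically meaningful and related with the specific" exceptions that follow. One exception reads "Grade 3 rash, nausea, vomiting or diarrhea for ≤ 3 days or is not properly managed with optimal supportive care". Nothing else in the protocol defines or corrects its second limb, "or is not properly managed with optimal supportive care".

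The DLT count then drives escalation in three places:

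- Section 4.3, text: "If no DLT is encountered at a given dose level, escalation will be continued to the next higher dose level".
- Table 4-3, for 0 of 3 patients with a DLT: "Escalate dose to next higher dose level". With 1 of 3, at least three more patients are entered at the same level.
- Synopsis, Duration of Therapy, for the first six patients: "if those patients do not experience a DLT, an additional 6 patients will be enrolled at the next Dose level".

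Two further rules count grade 3 or higher treatment-associated events in the first 30 days and list no exceptions. The synopsis closes a dose level to new patients if "1 or more of the first 3 safety-evaluable patients experience grade 3 or higher treatment-associated adverse events". Section 5.2 does so only at two or more of the first six. Under Appendix 2, the monitoring committee's Chair or Vice Chair must approve each escalation.

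In section 4.3.3, Table 4-5 has a row headed "Any toxicity, if clinically significant and not manageable by supportive care", which covers grades 2 and 3 and leads to interruption of epacadostat and pembrolizumab.

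**The concern.** An exception to a DLT definition normally removes events that say little about the dose. The first limb here, short duration, does that. The second limb is joined by "or" and sits inside the exception list, so it works independently of duration. Taken as written, poor management takes an event out of the count, and good management of a longer event leaves it in.

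The lead-in's primary objective is safety, and the epacadostat dose it selects is carried into Arm A (Table 4-2). If investigators at different sites read the clause differently, the same clinical course produces different DLT counts and so different escalation decisions.

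**Working it through.** The protocol states no operating characteristic for the DLT rule, so there is no figure of its own to reproduce. The check has a rule trace and an illustration.

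**Rule trace.** Take one patient among the first three with a related, clinically meaningful grade 3 diarrhea that lasts more than three days despite optimal supportive care.

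| Rule | If the phrase means care failed | If it means optimal care was not given |
|---|---|---|
| 4.3.1 | exempt | counts |
| Table 4-3 | 0/3, escalate | 1/3, add three patients |
| 5.2 (2 or more of 6) | no halt | no halt |
| Synopsis (1 or more of 3) | halt if within 30 days | halt if within 30 days |

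With two or three such patients, the first reading still gives 0/3 and escalation. The second gives 2/3 or 3/3, and Table 4-3 stops escalation. Both halt rules would then act, provided the events fall within 30 days. The DLT window is Cycle 1, which is 42 days in Table 3-1, although Table 4-1 refers to 28-day cycles. On the 42-day calendar, an event after day 30 lies outside both halt rules.

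**Event rates.** The documents give no rate for the disputed events in this triplet. The nearest figures are in section 1.2.2, for epacadostat 100 mg BID with pembrolizumab. Among 18 + 99 = 117 patients, treatment-related grade 3 or higher rash occurred in 5 (5/117 = 4.3%) and nausea in 2 (2/117 = 1.7%). I use these two rates, and 20% as a high value, all as assumptions for e, the chance that a patient has a disputed event.

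The chance of at least one such event in n patients is 1 − (1 − e)^n:

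| e | n = 3 | n = 6 |
|---|---|---|
| 1.7% | 1 − 0.983³ = 5% | 1 − 0.983⁶ = 10% |
| 4.3% | 1 − 0.957³ = 12% | 1 − 0.957⁶ = 23% |
| 20% | 1 − 0.8³ = 49% | 1 − 0.8⁶ = 74% |

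**Effect on escalation.** Under Table 4-3 a level is passed with 0/3, or with 1/3 followed by 0/3. With p the DLT probability per patient and q = 1 − p, P(escalate) = q³ + 3pq² × q³. Assume other DLTs occur in 10% of patients, and that a patient has either another DLT or a disputed event but not both, so that the rates add.

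| Disputed events | p | q³ + 3pq⁵ | Difference from exempt |
|---|---|---|---|
| Exempt | 0.100 | 0.729 + 0.177 = 0.906 | – |
| Count, e = 1.7% | 0.117 | 0.688 + 0.188 = 0.877 | 0.029 |
| Count, e = 4.3% | 0.143 | 0.629 + 0.198 = 0.828 | 0.078 |
| Count, e = 20% | 0.300 | 0.343 + 0.151 = 0.494 | 0.412 |

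Components are rounded separately. These figures apply Table 4-3 alone, without the halt rules or committee approval.

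**The case against.** The strongest reply is that the wording describes the adequacy of the care given. On that view an event that never received optimal care is not a fair test of the dose, while one that persists despite optimal care is a DLT. This is a possible reading, and it rules out the stronger inference that the protocol definitely exempts events that supportive care fails to control. It does not rescue the clause. The text does not say which meaning applies, and on this reading too a poorly managed event is exempt without limit of duration.

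A reader might also infer that Table 4-5 contradicts section 4.3.1. It does not do so directly. It uses a different phrase, governs interruption rather than DLT status, and includes grade 2, which cannot be a non-hematologic DLT. It shows only that the protocol elsewhere treats toxicity beyond supportive care as a reason to act.

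Nor do the documents support the inference that escalation would go unchecked. The halt rules would catch many of these events. The report to the committee Chair before escalation covers all adverse events as well as DLTs, and the exemption does not reach grade 4. That much of the objection stands. The safeguards still leave a gap: the two halt rules have different thresholds, both end at 30 days, and the DLTs in the committee report are those the protocol defines. The absence of exceptions in the halt rules affects every item on the exception list, so it says nothing about the direction of this one.

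Finally, a 20% event rate has no support in the documents. The 1.7% and 4.3% figures are the only anchor and an imperfect one. They cover all related grade 3 or higher events of each type, of which poorly managed ones are a subset, but they come from a lower epacadostat dose without tavo-EP.

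**Conclusion.** The clause is wrong as written. It is ambiguous, and it lets management quality, rather than severity or duration, remove an event from the DLT count. A single patient in three is enough to change the Table 4-3 decision from adding three patients to escalating. In that case section 5.2 would not halt, and the synopsis rule would do so only for an event within 30 days.

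The size is uncertain. Under the assumptions above, exempting the events raises the chance of passing a dose level by about 3 percentage points at an event rate of 1.7%, 8 at 4.3% and 41 at 20%. Where the halt rules are also applied, the practical effect is smaller. The existence of the defect does not depend on any of these rates, and no efficacy sample size, power or type I error figure is affected.

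**What to change.** The sponsor's clinicians should restate the exception so that it is clear whether managed or unmanaged events are exempt, and whether duration applies to both limbs. The restated clause should be reconciled with these passages:

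- the lead-in halt rules in the synopsis and section 5.2, including their different thresholds and their 30-day limit against the Cycle 1 DLT window;
- section 4.3.2, which allows dose modification in Cycle 1 only after a DLT, against the grade 3 diarrhea row of Table 4-5, which calls for epacadostat to restart at a reduced dose. Both cannot be followed for grade 3 diarrhea in Cycle 1 that is exempt from DLT status;
- the Table 4-5 row on toxicity that supportive care cannot manage.

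The aim is one definition and one observation window for escalation. Which clinical rule is right is for the clinicians, and none is proposed here. The cost is amendment wording, and possibly more events classified as DLTs.

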4.3.2 Dose Modifications and Management of Toxicity

Dose modifications are permitted in Cycle 1 only in the event of a DLT.

Dose modifications of epacadostat will be made per the dose escalation table.

1. If dose reduction of epacadostat is necessary:

- The dose should be reduced stepwise based on the dose escalation table. The patient should be monitored for approximately 10 to 14 days at each dose level.

Treatment or visit delays for public holidays or weather conditions do not constitute a protocol violation. After cycle 2, patients who have benefit are allowed to request treatment interruptions for personal reasons up to three weeks. Longer treatment interruptions must be approved by the PI and the drug sponsor.

The following dose modification rules will be used with respect to potential toxicity. Toxicity will be assessed according to the NCI Common Terminology Criteria for Adverse Events Version 4.03 (CTCAE v4.03).

4.3.3 Treatment Modification – All Agents

Adverse events associated with treatment on study may be immune-related or not immune-related. Immune-related AEs (irAEs) may be predicted based on the nature of the compounds, their mechanism of action, and reported experience with immunotherapies that have a similar mechanism of action. Special attention should be paid to AEs that may be suggestive of potential irAEs. An irAE can occur shortly after the first dose or several months after the last dose of treatment. If an irAE is suspected, efforts should be made based on the investigator's clinical judgment to rule out neoplastic, infectious, metabolic, toxins, or other etiologic causes prior to labeling an AE as an irAE.

In some circumstances, it may be necessary to temporarily interrupt pembrolizumab, tavo-EP or epacadostat as a result of AEs that may have an unclear relationship to any individual study drug. If an interruption for an adverse event is necessary and the causative agent cannot be identified, all agents should be interrupted. Immune-related adverse events may also be attributable to epacadostat alone, pembrolizumab alone, tavo-EP, alone or the combination of two or three of these agents. If the event is clearly related to one of the agents, follow the instructions specific for that agent. If the event is related to more than one agent, follow the action taken instructions for each causative agent.

General supportive care recommendations to manage irAEs are detailed in *Table 4-4*. Additional treatment modification recommendations may be found in subsequent sections, in the pembrolizumab package insert, and in the investigator's brochures for epacadostat and tavo-EP.

Table 4-4: General Guidelines for Immune-Related Adverse Events

irAE Toxicity Grade	Withhold/Discontinue Agent(s)	Action Taken With Respect to Agent(s)	Supportive Care
Grade 1	No action.	Not applicable.	Provide symptomatic treatment.

Grade 2	May withhold agent per investigator's discretion.	Not applicable. Investigators discretion.	Consider systemic corticosteroids in addition to appropriate symptomatic treatment.
Grade 3	Withhold or discontinue agent(s). Discontinue if unable to reduce corticosteroid dose to < 10 mg/day of prednisone or equivalent within 6 weeks of toxicity.	Return to treatment if improves to Grade 1 or resolves within 6 weeks. If AE resolves within 4 weeks, subject may restart at the same dose and schedule for epacadostat. For an AE that does not resolve within 4 weeks, agent(s) should be reduced 1 dose level. If AE does not resolve within 6 weeks, study treatment with agent(s) should be discontinued or discussed with principal investigator.	Systemic corticosteroids are indicated in addition to appropriate symptomatic treatment. May use 1-2 mg/kg prednisone or equivalent per day. Steroid taper should be considered once symptoms improve to ≤ Grade 1 and tapered over at least 4 weeks in most cases.
Grade 4	Discontinue agent(s).	Not applicable. Any exceptions require principal investigator approval.	Systemic corticosteroids are indicated in addition to appropriate symptomatic treatment. May use 1-2 mg/kg prednisone or equivalent per day. Steroid taper should be considered once symptoms improve to ≤ Grade 1 and tapered over at least 4 weeks in most cases.

Any interruptions of > 2 weeks or for LFT abnormalities must be discussed with the principal investigator before resuming treatment. Treatment with epacadostat, pembrolizumab, and tavo-EP should be withheld for drug-related Grade 4 hematologic toxicities, non-hematological toxicity ≥ Grade 3 (including laboratory abnormalities), and severe or life-threatening AEs.

Discontinuation Rules and Procedures for Specific Immune-Related Adverse Events Associated with Epacadostat and Pembrolizumab

Supportive care measures for the management of adverse events with potential immunologic etiology that are, in the judgment of the investigator, at least possibly associated with pembrolizumab and/or epacadostat are outlined in **Table 4-5** below and **Table 4-6** for pembrolizumab infusion-related reactions. For AEs listed in **Table 4-5** and **Table 4-6**, follow the guidelines in **Table 4-5**, and **Table 4-6**. For AEs not listed in **Table 4-5** or **Table 4-6**, follow the guidelines in **Table 4-4**. For each disorder listed in **Table 4-5**, and **Table 4-6** attempts should be made based in the investigator's clinical judgment to rule out other causes such as metastatic disease or bacterial or viral infection, which might require additional supportive care.

Table 4-5: Dose Modification Guidance for Epacadostat and Pembrolizumab

Adverse Event	CTCAE v4.03 Grade	Action Taken
Adrenal Insufficiency	2	
Hold pembrolizumab and epacadostat until patient is clinically stable. Treat with corticosteroids. If toxicity worsens, then treat as Grade 3 or Grade 4. Pembrolizumab and epacadostat can be resumed once event stabilizes and after completion of steroid taper.
 
Patient can be retreated with study drug/study regimen on the following conditions:
 
 1. The event stabilizes and is controlled. 2. The patient is clinically stable as per investigator or treating physician's clinical judgement. 3. Doses of prednisone are ≤ 10 mg/day or equivalent.
	3 or 4	
Hold pembrolizumab and epacadostat until patient is clinically stable. Treat with corticosteroids. Pembrolizumab and epacadostat can be resumed once event stabilizes and after completion of steroid taper.
 
Patient can be retreated with study drug/study regimen on the following conditions:
 
 1. The event stabilizes and is controlled. 2. The patient is clinically stable as per investigator or treating physician's clinical judgement. 3. Doses of prednisone are ≤ 10 mg/day or equivalent.

Adverse Event	CTCAE v4.03 Grade	Action Taken
Diarrhea/colitis	1	Subjects should be carefully monitored for signs and symptoms of enterocolitis (such as diarrhea, abdominal pain, blood, or mucus in stool, with or without fever) and of bowel perforation (such as peritoneal signs and ileus). Continue treatment with epacadostat and pembrolizumab, and initiate supportive care measures, which include drinking liberal quantities of clear fluids. If sufficient oral fluid intake is not feasible, fluid and electrolytes should be substituted via IV infusion. An antidiarrheal can be started.
	2	Interrupt epacadostat and pembrolizumab, and initiate supportive care measures, which include drinking liberal quantities of clear fluids. If sufficient oral fluid intake is not feasible, fluid and electrolytes should be substituted via IV infusion. An antidiarrheal should be started. When diarrhea resolves to baseline, restart epacadostat and pembrolizumab at the same dose.
	3	Interrupt epacadostat and pembrolizumab. When diarrhea resolves to baseline, resume pembrolizumab and restart epacadostat at a reduced dose. Monitor subjects for signs and symptoms of enterocolitis (such as diarrhea, abdominal pain, mucus or blood in stool, with or without fever) and of bowel perforation (such as peritoneal signs and ileus). In symptomatic subjects, rule out infectious etiologies and consider endoscopic evaluation for persistent or severe symptoms. For recurrent or persistent Grade 3 diarrhea, consider further dose reduction of epacadostat, or discontinuation of pembrolizumab and epacadostat.
	4	Discontinue epacadostat and pembrolizumab
Pneumonitis	2	Interrupt epacadostat and pembrolizumab and initiate systemic corticosteroids. Taper as necessary. May return to study treatment if condition improves to \leq Grade 1. Permanently discontinue if toxicity does not resolve within 12 weeks of last dose or if subject shows inability to reduce corticosteroid to \leq 10 mg prednisone or equivalent per day within 12 weeks.

Adverse Event	CTCAE v4.03 Grade	Action Taken
	3 or 4	
Permanently discontinue epacadostat and pembrolizumab. Immediately treat with intravenous corticosteroids. Administer additional anti-inflammatory measures, as needed.
 
Add prophylactic antibiotics for opportunistic infections in the case of prolonged steroid administration.

Type I diabetes mellitus (TIDM; if new onset, including diabetic ketoacidosis [DKA]) or \geq Grade 3 hyperglycemia, if associated with ketosis (ketonuria) or metabolic acidosis (DKA)	Newly onset TIDM or Grade 3 or 4	
Insulin replacement therapy is recommended for Type I diabetes mellitus and for Grade 3-4 hyperglycemia associated with metabolic acidosis or ketonuria.
 
Evaluate subjects with serum glucose and a metabolic panel, urine ketones, glycosylated hemoglobin, and C-peptide.
 
Once serum glucose is stabilized, pembrolizumab, tavo-EP and epacadostat should restart at the same dose if the episode is thought to be unrelated to treatment. If the episode is related, resume treatment with a one level dose reduction of epacadostat.

Hypophysitis	2	
Hold pembrolizumab and epacadostat. Treat with oral corticosteroids. When symptoms improve to \leq Grade 1, steroid taper should be started and continued over no less than 4 weeks. Replacement of appropriate hormones may be required as the steroid dose is tapered.

	3 or 4	
Discontinue epacadostat and pembrolizumab. Treat with an initial dose of IV corticosteroids followed by oral corticosteroids. When symptoms improve to Grade 1 or less, steroid taper should be started and continued over no less than 4 weeks. Replacement of appropriate hormones may be required as the steroid dose is tapered.

Hyperthyroidism or hypothyroidism	2	
Thyroid disorders can occur at any time during treatment. Monitor subjects for changes in thyroid function (at the start of treatment, periodically during treatment, and as indicated based on clinical evaluation) and for clinical signs and symptoms of thyroid disorders.
 
In hyperthyroidism, nonselective beta-blockers (eg, propranolol) are suggested as initial therapy.
 
In hypothyroidism, thyroid hormone replacement therapy, with levothyroxine or liothyronine, is indicated per standard of care.

Adverse Event	CTCAE v4.03 Grade	Action Taken
	3 or 4	
In hypothyroidism, thyroid hormone replacement therapy, with levothyroxine or liothyronine, is indicated per standard of care.
 
In hyperthyroidism, treat with an initial dose of IV corticosteroid followed by oral corticosteroids. When symptoms improve to \leq Grade 1, steroid taper should be started and continued over no less than 4 weeks.
 
Replacement of appropriate hormones may be required as the steroid dose is tapered. Once hyperthyroidism has resolved and steroids tapered, subject may resume epacadostat, pembrolizumab and tavo-EP or permanently discontinue at the discretion of the investigator.

Hepatic	2	
Hold pembrolizumab and epacadostat. Monitor liver function tests more frequently until returned to baseline values (consider weekly or twice weekly if steroids are not initiated). Treat with IV or oral corticosteroids.

	3 or 4	
Permanently discontinue pembrolizumab and epacadostat if related to these agents. Treat with intravenous corticosteroids. When liver chemistry tests improve to \leq Grade 1, a steroid taper should be started and continued over no less than 4 weeks. If unrelated to pembrolizumab, treatment with pembrolizumab and epacadostat may be resumed once steroids have been discontinued.

Myocarditis	2	
Hold pembrolizumab and epacadostat until resolution to Grade 0. Monitor symptoms daily, hospitalize. Promptly start IV methylprednisolone 2 to 4 mg/kg/day or equivalent after Cardiology consultation has determined whether and when to complete diagnostic procedures including a cardiac biopsy. Once the patient is improving, gradually taper steroids over \geq28 days and consider prophylactic antibiotics, antifungals, or anti-PJP treatment (refer to current NCCN guidelines for treatment of cancer-related infections [Category 2B recommendation]). If toxicity rapidly improves to Grade 0, then the decision to reinitiate study drug/study regimen will be based upon treating physician's clinical judgment and after completion of steroid taper. If toxicity does not rapidly improve, permanently discontinue pembrolizumab and epacadostat.

Adverse Event	CTCAE v4.03 Grade	Action Taken
	3 or 4	Permanently discontinue pembrolizumab and epacadostat if related to these agents. Monitor symptoms daily, hospitalize. Promptly start IV methylprednisolone 2 to 4 mg/kg/day or equivalent after Cardiology consultation has determined whether and when to complete diagnostic procedures including a cardiac biopsy. Once the patient is improving, gradually taper steroids over \geq 28 days and consider prophylactic antibiotics, antifungals, or anti-PJP treatment (refer to current NCCN guidelines for treatment of cancer-related infections [Category 2B recommendation]).
Renal failure or nephritis	2	Treat with oral corticosteroids.
	3 or 4	Permanently discontinue pembrolizumab and epacadostat if related to these agents. Treat with systemic corticosteroids. When severity of the event improves to \leq Grade 1, steroid taper should be started and continued over no less than 4 weeks. If unrelated to pembrolizumab, treatment with pembrolizumab and epacadostat may be resumed once steroids have been discontinued.
Any toxicity, if clinically significant and not manageable by supportive care	2 or 3	Interrupt epacadostat and pembrolizumab if toxicity is attributed to epacadostat and pembrolizumab. When toxicity resolves to \leq Grade 1, resume pembrolizumab and epacadostat. For recurrent or persistent Grade 2 or 3 toxicity that is clinically significant and not manageable with supportive care, consider further dose reduction of epacadostat or epacadostat and pembrolizumab discontinuation.
Other AEs	4	In general, epacadostat and pembrolizumab should be discontinued. Treatment with epacadostat and pembrolizumab may only be restarted after consideration of the benefit versus the risk and the approval of the principal investigator.

Procedures for Other Immune-Mediated Adverse Reactions, Including Ocular Manifestations

Epacadostat and pembrolizumab should be permanently discontinued for severe (Grade 4) irAEs. Systemic corticosteroids treatment should be initiated at a dose of 1 to 2 mg/kg per day of prednisone or equivalent for severe irAEs.

Corticosteroid eye drops should be administered to subjects who develop uveitis, iritis, or episcleritis. Epacadostat and pembrolizumab should be permanently discontinued for immune-mediated ocular disease that is unresponsive to local immunosuppressive therapy.

Dose modification and toxicity management of infusion-reactions related to pembrolizumab

Pembrolizumab may cause severe or life threatening infusion-reactions including severe hypersensitivity or anaphylaxis. Signs and symptoms usually develop during or shortly after drug infusion and generally resolve completely within 24 hours of completion of infusion. Dose modification and toxicity management guidelines on pembrolizumab associated infusion reaction are provided in **Error! Reference source not found.**

Table 4-6: Pembrolizumab Infusion Reaction Dose Modification and Treatment Guidelines

NCI CTCAE Grade	Treatment	Premedication at Subsequent Dosing
Grade 1 Mild reaction; infusion interruption not indicated; intervention not indicated	Increase monitoring of vital signs as medically indicated until the participant is deemed medically stable in the opinion of the investigator.	None
Grade 2 Requires therapy or infusion interruption but responds promptly to symptomatic treatment (e.g., antihistamines, NSAIDs, narcotics, IV fluids); prophylactic medications indicated for ≤24 hrs.	Stop Infusion. Additional appropriate medical therapy may include but is not limited to: IV fluids Antihistamines NSAIDs Acetaminophen Narcotics Increase monitoring of vital signs as medically indicated until the participant is deemed medically stable in the opinion of the investigator. If symptoms resolve within 1 hour of stopping drug infusion, the infusion may be restarted at 50% of the original infusion rate (e.g. from 100 mL/hr. to 50	Participant may be pre-medicated 1.5h (\pm 30 minutes) prior to infusion of _____ with: Diphenhydramine 50 mg po (or equivalent dose of antihistamine). Acetaminophen 500-1000 mg po (or equivalent dose of analgesic).

	
mL/hr.). Otherwise dosing will be held until symptoms resolve and the participant should be pre-medicated for the next scheduled dose.
 
Participants who develop Grade 2 toxicity despite adequate premedication should be permanently discontinued from further study drug treatment
	
Grades 3 or 4 Grade 3: Prolonged (i.e., not rapidly responsive to symptomatic medication and/or brief interruption of infusion); recurrence of symptoms following initial improvement; hospitalization indicated for other clinical sequelae (e.g., renal impairment, pulmonary infiltrates) Grade 4: Life-threatening; pressor or ventilatory support indicated	
Stop Infusion.
 
Additional appropriate medical therapy may include but is not limited to:
 
 • Epinephrine** • IV fluids • Antihistamines • NSAIDs • Acetaminophen • Narcotics • Oxygen • Pressors • Corticosteroids • Increase monitoring of vital signs as medically indicated until the participant is deemed medically stable in the opinion of the investigator. • Hospitalization may be indicated. • **In cases of anaphylaxis, epinephrine should be used immediately. 
Participant is permanently discontinued from further study drug treatment.
	No subsequent dosing

Appropriate resuscitation equipment should be available at the bedside and a physician readily available during the period of drug administration. For further information, please refer to the Common Terminology Criteria for Adverse Events v4.0 (CTCAE) at http://ctep.cancer.gov
		

Guidelines for Subjects Exhibiting Serotonin Syndrome

